9. STUDY ADMINISTRATION

9.1 Data Collection, Management and Confidentiality

Data will be collected by the study investigators using the above described sources and their personal usernames and passwords. Study investigators will be responsible for the data management and the accuracy of the records. Only the study team will have access to the

database. Data will be recorded on a Microsoft Excel spreadsheet and will be maintained in a locked digital file on the hospital's secure server. Data will be backed up on the hospital's secure server. Any research information obtained about the patient in this study will be kept confidential. A patient will not be identified by name, only by unique study ID number. The patient's name or any identifying information will not appear in any reports published as a result of this study. All identifying information will be kept behind 2 security measures or as per equivalent institutional policy, under the supervision of the study Principal Investigator and will not be transferred outside of the hospital. Relevant study records will be archived for 25 years following completion of the study, as per the requirements of Health Canada's Food & Drug Act, Part C Division 5. Once the study is complete and the final report has been published, the records will be retained and destroyed in accordance with The Hospital for Sick Children Record Retention and Destruction policy. All information collected in this study will be kept confidential in accordance with institutional policies on subject privacy and PHIPA. Investigators will not use data for any purpose other than conducting the study.

9.2 Data & Safety Monitoring Board (DSMB)

An independent DSMB of 4 members will monitor the progress of the study and review the safety data. The DSMB will review the result of analyses and other safety data and, if required, will provide recommendations to the study sponsor including to stop the trial if there are safety concerns.

9.3 Regulatory and Ethical Considerations

This study involves an experimental examination for pregnant women and fetuses using supplementary oxygen for a limited period of time. Based on earlier experiences by others and our center that includes the prolonged use of MH as a potential treatment for fetuses with single ventricle physiology, no fetal and maternal AEs occurred. However, data on the use of MH for fetal TGA is scarce and therefore fetal and maternal monitoring during oxygenation warranted. All participants will be made aware of the experimental aspects of this research, and the time of oxygen administration will be kept as short as possible and will be shorter than in previous studies. In the unlikely event of a serious complication attributable to the MH we will discontinue the study.

If any incidental findings occur during the study, the study team will share the atypical findings and provide recommendations with the SickKids physician. Clinical care will be provided as needed.

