In the event of an AE, we will use a variety of sources of information to identify possible side effects of the MH including direct observations, imaging data, participant reports, laboratory reports and other medical reports. The PI and study team will evaluate the circumstances and clinical correlation of the events. If a serious and unexpected AE occurs that is deemed to be possibly related to the use of MH (e.g. fetal death within a day of the oxygen administration), we will discontinue the use of supplementary oxygen to that study participant as applicable, immediately place the study on hold indefinitely, and the PI will report the case to the DSMB and Health Canada.

In the case of a moderate AE that is considered possibly related to the intervention (e.g. cardiac dysfunction such as fetal bradycardia of less than 90 beats per minute for more than 1 minute), we will discontinue the administration of oxygen in that study participant and the DSMB will review the event at their next scheduled meeting, and continue to enrol other patients for the study.

If an AE is mild, we will discontinue the oxygen supplementation to that study participant, but continue enrolling other patients for the study. Examples of mild maternal AEs that will result in discontinuation of oxygen administration for a subject will include fatigue, nasal or oral dryness or minor nasal bleeding and skin irritation.

In the event that oxygen supplementation is discontinued as a result of an AE, the study participant will not undergo oxygen supplementation at a later time and will be withdrawn from the study. Any data that is collected up until the point of withdrawal will be kept.

We do not expect ductal occlusion to occur within 45 minutes of fetal exposure to saturations that are lower when compared with a neonate. In the unlikely event ductal constriction occurs, it will be reversible once the MH is discontinued.

d) Expectedness assessment:

Unexpected	If the nature, severity or frequency of an event is not consistent with the risk information listed in the Material Safety Data Sheet
-------------------	---

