AEs and SAEs related to oxygen administration will be documented by the site investigator. Prior to the start of oxygen administration, a thorough medical history should be obtained to document all preexisting maternal symptoms, complaints and health concerns. As many pregnancy related symptoms are intermittent in nature, a thorough history including variations in severity and frequency should be taken. AEs and SAEs should be reassessed at each participant encounter. If signs or symptoms remain similar to baseline or are less in severity, frequency, or both, they will be considered within the usual range and do not need to be documented as AEs. In contrast, signs and symptoms that are new or, if preexisting, are more frequent/severe, need to be documented, assessed for severity and causality, and followed up until resolution.

In addition, the following table of endpoints will be used for the study:

Unexpected fetal demise	Stop the study; review by DSMB, PI and collaborators
Detection of cardiac dysfunction	Discontinue the exam – observe until resolved Review by PI and collaborators
Fatigue, dry/bloody nose, skin irritation	Review by PI and collaborators

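### The three study-halting rules in Sections 7 and 9.3 have different triggers and consequences, and no section says which prevails or who may lift a hold

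*Combined protocol and SAP*

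**What the plan says.** Study-level halting appears in four places in the protocol.

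- **Section 7, text.** The trigger is "If a serious and unexpected AE occurs that is deemed to be possibly related to the use of MH", with "fetal death within a day of the oxygen administration" given as an example. Besides stopping oxygen for that participant, the team will "immediately place the study on hold indefinitely, and the PI will report the case to the DSMB and Health Canada".
- **Section 7, table of endpoints.** For "Unexpected fetal demise" the action is "Stop the study; review by DSMB, PI and collaborators". The row has no relatedness condition and no time limit.
- **Section 9.3.** "In the unlikely event of a serious complication attributable to the MH we will discontinue the study". Expectedness is not mentioned, and no review comes before the decision.
- **Section 9.2.** The DSMB reviews safety data and may recommend to the sponsor that the trial stop. No trigger is given.

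At participant level, the Section 7 text says that for a moderate, possibly related AE (the example is fetal bradycardia) oxygen is stopped and "the DSMB will review the event at their next scheduled meeting". The table row for cardiac dysfunction ends the exam, asks for observation, and then gives "Review by PI and collaborators". For mild maternal AEs the text stops oxygen and, in a later paragraph, withdraws any participant whose oxygen was stopped for an AE. The table row for the same kinds of symptom lists only review.

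**The concern.** Halting rules should give one answer before an event happens. Here the triggers differ on three conditions: relatedness (possibly related, none, attributable), expectedness (required in both parts of Section 7, absent from Section 9.3) and event type (any serious AE, fetal demise only, any serious complication). The stated consequences are a hold, a stop with review, and discontinuation.

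If a serious event occurs, the people running the study would have to choose among these rules after the fact, knowing the event and how far recruitment has gone. Section 8 describes the study as one of feasibility and safety, and Section 9.3 says that data on MH in fetal TGA are scarce, so the halting decision is part of what the study must do well.

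The participant-level differences matter less, but they bear on data completeness. MH is given on two occasions (Section 2.3), and recruitment runs until 50 have completed the study (Section 5.2). Under the Section 7 text, a mild AE at the first exam costs the second exam and a completer. The table does not say so.

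**Working it through.** The plan gives no numerical stopping boundary, so there is no figure to reproduce. The check applies each rule to the same events.

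**Step 1. Conditions of each rule**

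| | Section 7 text | Section 7 table | Section 9.3 |
|---|---|---|---|
| Event | Any serious AE | Fetal demise | Any serious complication |
| Must be unexpected? | Yes | Yes | No |
| Relatedness to MH | At least possibly related | None required | Attributable |
| Consequence | Indefinite hold | Stop, then review | Discontinue |
| Who is named | PI reports to DSMB and Health Canada | DSMB, PI, collaborators | Nobody |

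**Step 2. Five events under the three rules**

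| Event | Section 7 text | Section 7 table | Section 9.3 |
|---|---|---|---|
| A. Serious, unexpected, attributable; not a fetal demise | Hold | No study-halting row | Discontinue |
| B. Unexpected fetal demise, attributable | Hold | Stop, then review | Discontinue |
| C. Unexpected fetal demise, only possibly related | Hold | Stop, then review | Unclear |
| D. Unexpected fetal demise, judged unrelated | Not triggered | Stop, then review | Not triggered |
| E. Serious, attributable, expected; not a fetal demise | Not triggered | No study-halting row | Discontinue |

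**Step 3. Reading the table**

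- A and B are the clearest conflict: one event has both a hold and a termination as its stated consequence.
- C is unclear because *attributable* is not one of the five causality grades in Section 7 (definitely, probably, possibly, unlikely, unrelated). The protocol does not say which grades count.
- D depends on the table row alone. Fetal demise is also listed among the end points in the Protocol Summary, so an outcome that the study plans to record is, when unexpected, a stop trigger whatever its cause.
- E depends on Section 9.3 alone. Section 7 judges expectedness against the Material Safety Data Sheet, so a complication consistent with that sheet falls outside the Section 7 hold but not outside Section 9.3.

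**Step 4. What could settle it.** Sections 7, 9.2, 9.3 and 9.3.3 were checked for an order of precedence, a person or body who may lift a hold, and conditions for restarting. None is given. Section 9.2 gives the DSMB the power to recommend stopping and does not mention restart.

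**Illustration only.** The documents give no rate of fetal demise. If each fetus had an assumed probability p of an unexpected demise after MH judged unrelated (event D), the chance of at least one among 50 is 1 − (1 − p)^50:

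- p = 0.2%: 1 − 0.998^50 = 9.5%
- p = 0.5%: 1 − 0.995^50 = 22.2%
- p = 1%: 1 − 0.99^50 = 39.5%
- p = 2%: 1 − 0.98^50 = 63.6%

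These figures show how often the table row might apply on assumed rates. They do not measure the conflict, and the conclusion does not use them.

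**The case against.** The strongest reply is that the rules add up. Section 7 introduces its table as additional to the text, so whichever trigger is met applies, and the text's silence on an event is not a decision to carry on. This largely stands for event D: on the additive reading an unrelated but unexpected demise simply stops the study for review. A reader might infer that the same event could stop, pause or leave the study untouched, but the documents do not go that far.

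A stop followed by review may also mean the same as a hold reported to the DSMB. That is possible, so no firm contradiction between the text and table of Section 7 on pause versus termination is claimed. A reader might likewise infer that one unrelated demise ends the study for good; the table does not say that its stop is final.

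Three further inferences should be resisted.

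- The one-day interval after oxygen is only an example of a possibly related death, not a formal window.
- Serious events would not go unreported. Section 9.2 keeps DSMB review of safety data, and Section 9.3.3 sends unanticipated problems to the REB and serious unexpected reactions to Health Canada within 15 or 7 days.
- The cardiac and mild-AE rows do not bear on halting the study. They differ from the text on participant-level action and named reviewer. The table does not say that oxygen continues after a mild AE, and omitting the DSMB from one cell does not remove its general review.

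The additive reading does not cure Section 9.3. Adding the rules together still gives event A a hold and a termination, and still leaves open who may lift a hold.

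**Conclusion.** The concern holds as an internal inconsistency in the wording. The firm part is that a serious, unexpected, MH-attributable event is a hold in Section 7 and a termination in Section 9.3; that a serious, attributable but expected complication ends the study only under Section 9.3; that an unexpected, unrelated fetal demise stops it only under the table; and that no section ranks the rules or assigns the power to restart. The participant-level differences are secondary.

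The conclusion rests on reading discontinuation of the study in Section 9.3 as termination, which is its ordinary meaning. If the sponsor meant a hold there too, the wording still needs to say so, and the differences in trigger remain. No sample size, estimate or error rate changes. The size of the problem is the set of event classes without a single answer, not a probability. Which rule is clinically right is not judged here.

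**What to change.** Reconcile the Section 7 text, the Section 7 table, Section 9.2 and Section 9.3 into one rule set, and have each section refer to it. For each event class state:

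1. one trigger, saying whether relatedness is required (using the Section 7 causality grades), whether expectedness is required, and whether any time window applies;
2. one consequence, hold or termination, in the same words throughout;
3. one reviewing body;
4. who decides on restart, and on what basis.

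Use the same table for the participant-level rows, so that the DSMB's part in cardiac events and the handling of oxygen and withdrawal after mild AEs are each stated once. The sponsor and the DSMB choose which rule stands.

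The cost is protocol wording and DSMB agreement. No extra data or participants are needed.

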9.3.1 Informed Consent

The study is explained to the patient in detail, including the alternatives to be followed up without participation. Any study related questions will be answered prior to signing the consent form. The person obtaining consent must co-sign the form with date and time. A copy of the consent form must be given to the patient.

9.3.2 Study Withdrawal

A subject is free to withdraw from participation in the trial at any time, for any reason, specified or unspecified, and without prejudice. If the subject withdraws, data that has already been

collected up to that point in time will be kept (as indicated in the patient informed consent).

9.3.3 Reporting of Adverse Events and Serious Adverse Events

Subjects will be carefully monitored throughout their study participation. They should stop at any time they start to feel uncomfortable; even if they feel as though their ailment is unrelated to study intervention. If any unanticipated problems related to the research involving risks to subjects or others happen during the course of this study these will be reported to the REB in accordance with SickKids Policy. AEs that are not serious but that are notable and could involve risks to subjects will be summarized in narrative or other format and submitted to the REB at the time of continuing review.

All serious, unexpected adverse drug reactions to the study medication will be reported to Health Canada within 15 calendar days or for death or life-threatening events, within 7 calendar days. In the latter case, a follow-up report must be filed within 8 calendar days.

10. PUBLICATION

It is expected that study results will be published in peer reviewed papers. Individual authorship will be based on the investigator's contribution to a study component and journal guidelines of authorship. As per the International Committee of Medical Journal Editors (<http://www.icmje.org/recommendations/browse/roles-and-responsibilities/defining-the-role-of-authors-and-contributors.html>) authorship will be based on these 4 criteria: a) Substantial contributions to the conception or design of the work; or the acquisition, analysis, or interpretation of data for the work; AND b) Drafting the work or revising it critically for important intellectual content; AND c) Final approval of the version to be published; AND d) Agreement to be accountable for all aspects of the work in ensuring that questions related to the accuracy or integrity of any part of the work are appropriately investigated and resolved.

